Examining the Effect of Salbutamol Use in Asthma and/or EIB

Whilst Exercising in Ozone Air Pollution

Principal Investigator: [name] (MD, PhD)

Graduate Student: [name] (BKin)

Introduction

Physical activity has been recognized as an important component of a healthy lifestyle. This is especially true in developed regions of the world where sedentary behaviour has been associated with health conditions such as type 2 diabetes, hypertension, mood disorders, and certain types of cancer (De Rezende et al., 2014). As the world's population continues to develop, industrialization and urbanization have led to a larger number of people living in areas with increased ambient air pollution (Barbera et al., 2010). Exposure to air pollutants, such as particulate matter and ozone, have been associated with increased mortality and hospitalization due to cardiovascular and respiratory disease (Brunekreef & Holgate, 2002). This presents a potential issue because increased ventilation during exercise results in a proportionate increase in the amount of inhaled air pollution (Carlisle & Sharp, 2001). This issue is particularly relevant for individuals with asthma and/or exercise induced bronchoconstriction (EIB) who are more sensitive to respiratory irritants such as ozone (Guarnieri & Balmes, 2014). β_2 agonists, including salbutamol, are commonly prescribed to this population and their use is increased in regions with higher levels of ozone pollution (Pepper et al., 2020). However rodent studies have indicated potential negative consequences of β_2 agonists including increased protein leakage and lung inflammation (Henriquez et al., 2019). Therefore, further research is required on the effects of using β_2 agonists in ozone air pollution by people with asthma and/or EIB.

Background

Ozone gas is produced when volatile organic compounds and gases from the NO_x family found in smog react with ultraviolet (UV) radiation from the sun. This means that ozone pollution is more prominent during sunny weather due to increased levels of UV radiation (Sillman, 2003). As a result, when the weather is nice and people are more inclined to exercise outside, ozone

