Salbutamol is a short-acting β_2 agonist that works by binding to β_2 adrenergic receptors leading to increased sympathetic output to the lungs resulting in bronchodilation. Typically, individuals with EIB will take salbutamol 15 minutes before exercising (Jartti, 2001). This is potentially beneficial when exercising in ozone because it would counter the increased parasympathetic output caused by ozone exposure. However, a study conducted by Gong et al. showed that inhaled salbutamol did not decrease ozone-related pulmonary function impairment in healthy individuals compared to placebo after exercising in ozone (1988). This suggests that the primary mechanism of impaired lung function due to ozone may be related to inflammation rather than bronchoconstriction. It is not known if ozone exacerbates bronchoconstriction specifically in people with asthma and/or EIB exercising in ozone, but since bronchoconstriction could occur anyway in this population during exercise, regardless of ozone, β_2 agonists may still be beneficial.

A potential issue of salbutamol use in ozone relates to its effect on inflammation (Henriquez et al., 2019). Recent rodent studies by Henriquez et al. have shown that inflammatory cytokine levels, after exposure to ozone, are higher in rodents that were given a β_2 agonist compared to placebo (2019). This could potentially be related to salbutamol's known ability to increase fluid transport across the alveolar membrane (Perkins et al., 2006). However, it is not known if β_2 agonist use in humans would have the same effect. If the same effect does indeed occur in humans, it is also unknown whether increases in inflammation greater in asthma/EIB compared to healthy individuals. It is important to learn if salbutamol use exacerbates airway inflammation because chronic airway inflammation in people with asthma has been related to airway remodelling that increases the severity of future asthma attacks (Brightling et al., 2012). As a result, significant increases in airway inflammation, despite potential improvements in

immediate pulmonary function, may be a reason for contraindication of salbutamol use in people with asthma and/or EIB when exercising in ozone air pollution.

Objective

- Determine if using salbutamol before exercising in ozone air pollution is harmful for individuals with asthma and/or EIB because of increased airway inflammation.

Hypothesis

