Rating of symptoms (dyspnea, cough, sore throat, headache, chest pain, and chest tightness) and blood pressure will also be measured. The selected symptoms were chosen because they have been recognized or are related to symptoms of ozone exposure (Lippmann, 1989). Dyspnea will be measured subjectively using a modified Borg scale that has previously been used to measure dyspnea and validated against other dyspnea measures (Gaber et al., 2019). The other symptoms will be subjective rated on a scale from 0-5. Blood pressure will be measured using an automated sphygmomanometer. In accordance with Hypertension Canada's guidelines on blood pressure measurement, blood pressure will be measured three times and the first measure will be thrown away while the latter two are averaged (Nerenberg et al., 2018).

Study Design

This research design can be characterized as a placebo-controlled crossover design with pre-post measures. There are two independent variables: ozone pollution status and medication status. The two levels of ozone pollution status are 170 ppb ozone and room air. The two levels of medication status are 200 µg of salbutamol and placebo medication. Participants will perform 30 minutes of submaximal exercise at 60% of their $VO_{2\max}$ in all four conditions. These conditions are salbutamol + ozone, placebo + ozone, salbutamol + room air, and placebo + room air. The order of the conditions on the experimental days will be randomized to one of four sequences. The four conditions will be labelled A (ozone + inhaler A), B (ozone + inhaler B), C (room air + inhaler A), and D (room air + inhaler B). The researchers will not know which inhaler (A or B) is placebo

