Participants will visit the lab on five occasions. It will also be expected that participants will take no leukotriene modifier medication (Singulair or Montelukast) 24 hours before each visit, no short acting beta agonists 8 hours before each visit, no long acting beta agonists 48 hours before each visit, and no anti-histamines 72 hours before each visit. These pre-visit restrictions control for potential confounding effects on the eucapnic voluntary hyperpnea (EVH) test and FeNO measurement. Participants will be asked to avoid supplementation with vitamin C, vitamin E, and multivitamins over the course of the 5 visits. This prevents changes in the response to ozone related to vitamin supplementation (Gomes et al., 2011). Finally, participants will be asked to avoid exercise 24 hours before each lab visit. This is to ensure there is no diminishment in asthma and/or EIB severity related to a refractory period following exercise (Stickland et al., 2012). Day one will be a screening day and will involve: obtaining consent, collecting height, weight, age, and sex, screening participants for EIB, conducting a $\text{VO}_{2\text{max}}$ test, and orienting participants to FeNO and spirometry measurement. Participants will re-read and sign a consent form in addition to reviewing and signing a PAR-Q+. They will then do practice spirometry and FeNO measurements to orient themselves to the procedure of these measures. Then, participants will complete a EVH test to screen for EIB. The EVH test requires participants to voluntarily hyperventilate regular air that has a higher than normal CO_2 concentration for 6 minutes to replicate breathing during exercise. This mimics the stimulus that leads to airway narrowing in EIB (Hull et al., 2016). The higher than normal CO_2 concentration prevents CO_2 levels in the blood from dropping leading to loss of consciousness. Spirometry measures are obtained before and after EVH and compared. A 10% or greater decrease in FEV_1 will be used to confirm the presence of EIB (Hull et al., 2016). Participants will then take salbutamol at the treatment dose (200 μg and perform a $\text{VO}_{2\text{max}}$ test on a cycle ergometer. Performing a $\text{VO}_{2\text{max}}$ text will allow for the exercise intensity to be standardized

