Risks to participants related to physical harm for this study include: severe asthma attack, complications from maximal exercise, exposure to ozone, and salbutamol side effects. There will be a few instances during the study where participants will have a higher risk of having a severe asthma attack. These include the EVH test and the conditions where participants will be exercising in ozone. Having people with asthma and/or EIB exercise with placebo medication in the presence of a respiratory irritant could elicit an asthma attack (Balmes, 1993). Rescue medication, labelled salbutamol, the participant's own medication and oxygen will be kept nearby in the event of an emergency. Participants will also be reminded that they can stop the test at any time if breathing becomes too difficult. Potential complications of maximal exercise include: vomiting, abnormal blood pressure, fainting, heartbeat disorder, and rare instances of heart attack (Gibbons et al., 1989). To mitigate this risk, participants will fill out a PAR-Q+ on their first visit to the lab before signing the consent form. The PAR-Q+ is designed to screen for individuals that should speak to a physician before exercising (Warburton et al., 2018). Participants will be asked to immediately report any unusual symptoms during the test and be reminded that they may stop the test at any time. An automated external defibrillator (AED) will be present on site and researchers on site will be trained in standard first aid. Potential symptoms of exposure to ozone include cough, pain with inspiration, and shortness of breath (Lippmann, 1989). This risk will be mitigated by using a dose of ozone that does not exceed real-world levels of ozone exposure. This low dose of ozone will reduce the risk of experiencing symptoms from ozone exposure. In addition, this means that the

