risk related to ozone exposure would not exceed the level of risk that would occur in the daily lives of the participants. Participants will also have the ability to stop the exposure to ozone at any time. Some potential temporary side effects of salbutamol use include: nervousness, tremor, headache, dryness of the mouth, changes in taste or smell, cough, nausea, and dizziness. Some rare but serious side effects include: pounding heartbeat, chest pain, irregular heartbeat, rapid breathing, and confusion. Allergic reaction is rare but can result in rash, itchy tongue, severe dizziness, and trouble breathing (Burggraaf et al., 2001). This risk is avoided by only including participants in the study who have been prescribed salbutamol by their physician. A physician would not prescribe salbutamol if the side effects outweighed the benefits of the medication or the patient was allergic to the medication. If the participants do experience any serious side effects, immediate care will be provided by the researchers who are trained in standard first aid, and the participant will be taken to the nearest emergency room located approximately 250 meters away. On experimental days a physician will always be available to be onsite within ten minutes and at least one person collecting data will have a Standard First Aid with CPR/AED C certification. We have also created an emergency action plan and attached it to box 9.8.A of the application. This lab has a long track record of using this type of physician supervision with exercise studies in individuals with and without asthma, using higher intensity exercise, and even higher intensity exposures to air pollution like diesel exhaust ([H08-03055], [H09-01154], [H10-02028], [H10-00902], [H12-00539]). These studies have all been completed without incident. To ensure informed consent, a consent form will be sent to any individual interested in participating with enough time for them to review it and contact a member of the research team if they have any questions. This consent form will contain: the general purpose of the study and what the participant will be expected to do, foreseeable risks and potential benefits, alternatives to participation, contact information of the

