researcher, assurance that the participant can end their participation at any time, and contact information of the relevant research ethics board (TCPS 2, 2018). The relevant research ethics board for this study is the Clinical Research Ethics Board (CREB) which reviews clinical research done at the University of British Columbia. At the first lab visit, a printed version of the consent form will be provided for the participant to review and sign. Upon documenting consent there will be: a restatement of the study purpose and description of the study tasks, sufficient prompts to encourage participants to ask questions, a reminder of the participant's right to refuse anything they find disturbing or uncomfortable, an assurance of their right to leave at any time without penalty, a statement indicating that by signing the consent form the participant is not waiving any legal rights, and the provision of contact information of the researcher and CREB (TCPS 2, 2018).

Application of Findings

It is important to learn if salbutamol use exacerbates airway inflammation when exercising in ozone because chronic airway inflammation in people with asthma has been related to airway remodelling that increases the severity of future asthma attacks. In many cases, people with asthma and EIB are able to tolerate exercise without salbutamol use. This study will provide some information on whether this is a better strategy for preventing future more serious asthma attacks or not. This information can be used by physicians who prescribe salbutamol and by people with asthma and/or EIB.

Knowledge Translation

There are multiple stakeholders who may be interested in the results of this study including: clinicians, asthma and/or EIB patients, and air pollution policy makers. Publishing a paper in academic journals such as the European Respiratory Journal or the American Journal of

Respiratory and Critical Care Medicine would make this information available to clinicians and policy makers. Poster presentations at conferences such as the American Thoracic Society Conference would also enable communication of this information to clinicians and policy makers. Infographics that simplify the findings and recommendations could be used to communicate the information to non-expert stake holders such as patients with asthma and/or EIB. Web-based summaries, podcasts, and blogs could also be used to communicate this information to a larger population.

References

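### The daily-life ozone risk sentence rests on concentration alone and conflicts with its own section, and no FEV1 limit governs starting exercise

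*Combined protocol and SAP*

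**What the plan says.** **Risk statement.** Ethical Considerations reasons from a dose within real-world ozone levels to the conclusion that the "risk related to ozone exposure would not exceed the level of risk that would occur in the daily lives of the participants".

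**Same section, on asthma attacks.** It names the EVH test and the ozone exercise conditions as points of raised risk of a severe attack, and adds: "Having people with asthma and/or EIB exercise with placebo medication in the presence of a respiratory irritant could elicit an asthma attack".

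**Medication.** Study Design sets the sessions: "These conditions are salbutamol + ozone, placebo + ozone, salbutamol + room air, and placebo + room air". Procedures requires "no short acting beta agonists 8 hours before each visit, no long acting beta agonists 48 hours before each visit". On who takes part, Ethical Considerations says of salbutamol side effects: "This risk is avoided by only including participants in the study who have been prescribed salbutamol by their physician". Table 1 does not list that requirement. Background describes usual practice: "Typically, individuals with EIB will take salbutamol 15 minutes before exercising". The Introduction says β2 agonists "are commonly prescribed to this population and their use is increased in regions with higher levels of ozone pollution".

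**Order of events at an experimental visit (Procedures).** Inhaler, 15-minute wait, FeNO, blood pressure and symptoms, then spirometry, warm-up and 30 minutes of exercise. No FEV1 value is attached to the decision to start.

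**Rescue.** Salbutamol is kept at hand. Study Design continues measurement to 1 hour after exercise. The protocol refers to an emergency action plan filed in box 9.8.A of the ethics application.

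**The concern.** The risk to a person with asthma or EIB exercising in ozone depends on at least three things: concentration, ventilation and whether a bronchodilator has been taken. The daily-life sentence looks only at the first. In two of the four sessions participants exercise on placebo after their own bronchodilators have been withheld, and in one of those two they also breathe ozone. By the protocol's own account this departs from how such people usually exercise.

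The practical stake is safety. Staff are blinded to the inhaler, and as written they may start any participant whatever the FEV1 that day. Someone who arrives with narrowed airways can go straight into placebo + ozone.

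There is a lesser data question. Rescue is the study drug, and the protocol does not say how FEV1 values recorded after rescue are to be used.

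**Working it through.** **Step 1. The statements side by side.**

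| Topic | What the protocol says | Where |
|---|---|---|
| Ozone risk | Not above daily-life risk, because the dose is within real-world levels | Ethical Considerations |
| Ozone exercise conditions | Raised risk of severe asthma attack | Ethical Considerations |
| Placebo in an irritant | Could bring on an attack | Ethical Considerations |
| Usual behaviour with EIB | Salbutamol 15 minutes before exercise | Background |
| Study behaviour | Short-acting agents withheld 8 h, long-acting 48 h | Procedures |

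Row 1 cannot stand as a statement about risk next to rows 2 and 3. It can stand as a statement about concentration.

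**Step 2. How many sessions.** Sample and Recruitment plans 24 participants.
- All sessions: 24 × 4 = 96.
- Placebo sessions: 24 × 2 = 48.
- Placebo + ozone: 24 × 1 = 24.

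The figure of 24 reproduces. With a difference of 12, 14 read as the within-subject SD, SD of a difference 14 × √2 = 19.8 and a two-sided 0.05 paired t test, power at n = 24 is 0.811. Nothing below depends on it beyond the session count.

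**Step 3. What could act as a start check.** The only pre-exercise FEV1 at an experimental visit comes at least 15 minutes after the inhaler.
- On placebo days it is effectively an untreated value. The measurement exists; a limit on it does not.
- On salbutamol days it is a treated value. A limit on it would trigger less often than on placebo days, so the check would not be equal across conditions.

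**Step 4. What a limit would cost in postponed sessions.** For illustration, postpone if FEV1 is 10% or more below the visit-1 value taken before EVH. Assume independent, normal day-to-day variation with SD s; the documents give no s, so 4% to 6% is an assumption.
- Per session: P = 1 − Φ(10 / (s√2)).
- Per participant, four visits against one shared reference: P(at least one) = 1 − E[Φ(10/s − Z)⁴], with Z standard normal. The shared reference makes failures cluster, so this is lower than four independent tries would give.

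| s | Per session | Sessions of 96 | Participants, at least once | Of 24 |
|---|---|---|---|---|
| 4% | 0.0385 | 3.7 | 0.115 | 2.8 |
| 5% | 0.0786 | 7.6 | 0.212 | 5.1 |
| 6% | 0.1193 | 11.5 | 0.299 | 7.2 |

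These are first-attempt postponements caused by ordinary variation alone.

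**Step 5. Rescue.** The documents give no rescue rate, so only the direction follows. Rescue after placebo + ozone would raise later FEV1 values in that session and shrink the salbutamol–placebo difference at 30 minutes and 1 hour. The contrast immediately after exercise is largely untouched by post-exercise rescue. The effect on FeNO cannot be stated.

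**The case against.** **The risk is already disclosed.** Ethical Considerations lists asthma attack and ozone exposure as separate risks, and the daily-life sentence closes the ozone item, which is about cough, painful inspiration and shortness of breath. This largely stands. A reader might infer that the hazard was hidden from the ethics board; the documents do not support that. What remains is an inconsistency: the sentence speaks of risk, and in this population ozone risk cannot be separated from the attack risk described just before it. The consent form is not in the documents, so nothing can be said about what participants are told.

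**The measurement already exists where it matters most.** On placebo days the pre-exercise FEV1 is untreated in effect, and symptoms are recorded too. This stands. The gap there is a missing limit, not a missing test. A pre-inhaler reading is preferable only because it lets one limit work equally in all four conditions.

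**People often manage without salbutamol.** Application of Findings says: "In many cases, people with asthma and EIB are able to tolerate exercise without salbutamol use". That is fair, and Background speaks of what is typical of EIB, not of every participant. The remark makes no statement either way about tolerance in ozone.

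**Safeguards are in place.** Stopping at will, oxygen, a physician within ten minutes and a nearby emergency room are real, but they act once symptoms occur. PAR-Q+ screens at visit 1 only. A reader might infer that no stop or rescue triggers exist; the unseen emergency action plan may contain them.

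**The dose.** A reader might set 170 ppb against the cited one-hour limit of 100 ppb. Exposure lasts 30 minutes; with the other 30 at 10 ppb or less, the hourly mean is at most (170 × 30 + 10 × 30) / 60 = 90 ppb, ignoring exercise ventilation. The documents give no Greater Vancouver levels, so no claim is made that the dose exceeds them.

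**Conclusion.** The concern holds in two parts. The daily-life sentence is supported for concentration at most and is inconsistent, as a statement of risk, with the same section and with the withholding of bronchodilators. Separately, no FEV1 value governs starting exercise, so a participant with narrowed airways can begin any session, including the 24 planned placebo + ozone sessions.

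The missing rule for values after rescue is a minor omission. A reader might infer a loss of power from it, but that needs a rescue rate, which the documents lack, and a complete-case analysis, which they do not plan. It also depends on how the 14% is read: going from 24 to 20 participants would take power from 0.811 to 0.730 if 14% is the within-subject SD, but only from 0.980 to 0.953 if it is the SD of the paired difference. No power loss or size of bias is claimed.

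The postponement figures rest on the assumed SD of 4% to 6%, normality and a single visit-1 reference.

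**What to change.** 1. **Reword the risk sentence.** Limit the daily-life comparison to concentration. Add that exercising in 170 ppb ozone after placebo, with bronchodilators withheld, may carry a higher risk of an asthma attack than usual exercise with medication.
2. **Set an FEV1 start limit.** The study physician fixes it before the first participant. It applies blinded and identically in all four conditions, with postponement if it is not met and a cap on repeat postponements. Preferably base it on a brief spirometry before the inhaler, on the equipment already in use. At minimum, apply a limit to the existing pre-exercise spirometry. The protocol's 10% figure is a fall after EVH, so it is a starting point for discussion and not a validated day-to-day limit.
3. **Check the emergency action plan** for start, stop and rescue limits and copy any into the protocol.
4. **Minor:** record rescue salbutamol by time and condition, and show 30-minute and 1-hour FEV1 with and without post-rescue values.

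**Cost.** One ethics amendment. If the pre-inhaler test is adopted, 96 short spirometries at a few minutes each (assumed). They would come before FeNO, which is now taken first, but in the same way in every condition. Under the Step 4 assumptions, about 4% to 12% of sessions are postponed, affecting 11% to 30% of participants at least once. Each postponement repeats the drug withholding, which is why a cap is needed. The ozone dose, EVH entry rule and sample size are unchanged.

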- People with asthma and/or EIB who take salbutamol before exercising in ozone will have improved pulmonary function but higher levels of inflammation after exercise compared to placebo medication.

Methods

Sample and Recruitment

The target population for this study is individuals with asthma and/or EIB living in urban environments. The predicted sample representing this population will be people with asthma and/or EIB living in the Greater Vancouver area. The sample will be recruited by self-selection sampling. This will be accomplished through the use of posters on public advertising boards around campus at the University of British Columbia (UBC). A virtual form of the poster will also be posted on the UBC School of Kinesiology website and the in the UBC psychology graduate student council's newsletter. The poster and online advertisement will outline, in lay language, the purpose of the study, inclusion and exclusion criteria, the design of the study, the potential benefits and risks to the participants, and contact information to enroll in the study. Participants who hear of this study through word of mouth may also contact the research team if interested.

Table 1. List of study inclusion and exclusion criteria

Inclusion Criteria	Exclusion Criteria

 1) Have asthma and/or EIB related airway narrowing during exercise 2) Able to perform maximal exercise 3) Between 18 to 50 years of age 4) Able to communicate sufficiently using the English language 	
 1) Use inhaled corticosteroids 2) History of smoking 3) Chronic respiratory disease other than asthma or EIB 4) Upper respiratory tract infection within the last 4 months 5) Pregnant or potentially pregnant 6) Allergy to salbutamol

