As shown in **Table 1** above, there are four inclusion criteria for this study. The first criterion, diagnosed with asthma and/or EIB, represents the population of interest for this study. During the first lab visit, participants will perform a eucapnic voluntary hyperpnea test (see Procedures section) to be screened for airway narrowing triggered by exercise. The second inclusion criterion, able to perform maximal exercise, reduces the risk of physical harm by preventing participants who may be harmed by exercising from participating. Participants will be screened for this ability on the first day by filling out the physical activity readiness questionnaire (PAR-Q+). The third inclusion criterion, between 18 and 50 years of age, reduces the risk of physical harm by preventing people with age-related risks to ozone exposure from participating in the study. Compared to adults, the developing lungs of children and young adults are more susceptible to the oxidative stress of ozone which can cause life-long decrements in lung function (Goldizen et al., 2016). For this reason, only adults aged 18 and older will be included. Older adults, age greater than 65 years, are more susceptible to ozone-induced health effects compared to younger adults due to decreased physiological, metabolic, and compensatory processes (Shumake et al., 2013). An upper age limit of 50 years was chosen because we want to test a

relatively homogenous group with a reduced risk of occult medical conditions that may confound the findings. Furthermore, we have a long track record of conducting exercise and exposure studies in this age group without incident. As a result, only adults under the age of 50 and younger will be included. The final communication criteria, able to communicate sufficiently using the English language, ensures that participants will be able to fully understand the risks of the study and have any questions answered.

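### The risk section relies on enrolling only people prescribed salbutamol, but no eligibility criterion imposes that limit

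*Combined protocol and SAP*

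**What the plan says.** The Ethical Considerations section lists the temporary, the rare but serious, and the allergic effects of salbutamol. It then says "This risk is avoided by only including participants in the study who have been prescribed salbutamol by their physician", and gives its reason: "A physician would not prescribe salbutamol if the side effects outweighed the benefits of the medication or the patient was allergic to the medication".

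Eligibility is set out under Sample and Recruitment. The population is described by condition: "The target population for this study is individuals with asthma and/or EIB living in urban environments". The first inclusion criterion in Table 1 is "Have asthma and/or EIB related airway narrowing during exercise". The text below the table says "there are four inclusion criteria for this study" and explains the first of them in these terms: "The first criterion, diagnosed with asthma and/or EIB, represents the population of interest for this study". The other three inclusion criteria are ability to exercise maximally, age 18 to 50, and sufficient English. There are six exclusion criteria: inhaled corticosteroids, smoking history, other chronic respiratory disease, recent upper respiratory tract infection, pregnancy, and "Allergy to salbutamol".

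Under Procedures, every participant takes salbutamol at the treatment dose on day one, before the maximal exercise test. Under Study Design, two of the four later conditions also include salbutamol.

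**The concern.** The risk section presents the salbutamol risk as avoided by a restriction on who may enter. The eligibility list, which is what staff would apply at screening, does not contain that restriction. Applied as written, it could admit and dose a person to whom the claimed safeguard does not apply.

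Two things are at stake. First, an ethics board reading the risk section would believe in a protection that the criteria do not deliver. Second, the enrolled population is unclear: it may be people already prescribed salbutamol, or everyone with asthma and/or EIB who meets Table 1.

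**Working it through.** No formula applies. The check sets the risk section beside the eligibility criteria and counts.

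**1. Criteria that require a prescription.** Table 1 has 4 inclusion + 6 exclusion = 10 criteria, which matches the numbers in the explanatory text. Criteria requiring a salbutamol prescription: 0 of 10. Criteria mentioning salbutamol at all: 1 of 10 (exclusion 6, allergy). The explanations of the ten criteria add no prescription requirement.

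**2. Does the allergy exclusion do the same work?**

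| Ground given in the risk section | Listed salbutamol criterion that covers it |
|---|---|
| Physician judges that side effects do not outweigh benefits | None |
| Patient is not allergic | Exclusion 6 |

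The list covers 1 of the 2 grounds. The uncovered ground concerns the effects named apart from allergic reaction: 8 temporary (nervousness, tremor, headache, dry mouth, altered taste or smell, cough, nausea, dizziness) and 5 serious ("Some rare but serious side effects include: pounding heartbeat, chest pain, irregular heartbeat, rapid breathing, and confusion"), so 8 + 5 = 13. This count shows only what the uncovered ground refers to. The protocol does not claim that a prescription prevents these effects, and a prescribed user can still have them.

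**3. Does anything else impose the limit indirectly?**
- The PAR-Q+ is described as a screen for readiness to exercise, not for suitability for salbutamol.
- Short-acting beta agonists are withheld before visits, and the participant's own medication is kept nearby. Both fit a population that already uses such drugs, but neither is a condition of entry.
- The EVH test confirms EIB. It says nothing about prescriptions.
- The day-one procedure list mentions no prescription check. I give this no weight, because it describes no check for any of the six exclusion criteria either.

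**4. Exposure.** Day one plus two of the four conditions gives 1 + 2 = 3 planned salbutamol administrations per participant who completes all visits.

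**5. Number affected.** The documents do not say how many eligible volunteers would lack a prescription. With 24 planned subjects, the possible range is 0 to 24.

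**The case against.** The strongest reply is that the protocol should be read as a whole. The risk section is part of it and states the limit plainly, and nothing under Sample and Recruitment says that people without a prescription may enter. On that view Table 1 merely fails to repeat a rule. This is fair as to the kind of fault: the limit is not absent from the whole document. It does not remove the fault, because the explanatory text counts the criteria and works through them as a complete list. The poster and online advertisement are also to outline the inclusion and exclusion criteria to self-selecting volunteers.

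A second reply is that the risk said to be avoided could be allergic reaction alone, since the sentence just before concerns allergy. Exclusion 6 would then cover it. The wording leaves some room for this, but the sentence that follows names side effects before allergy, which favours the broader reading. The 1-of-2 result depends on that broader reading; the 0-of-10 result does not.

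Third, the target-population statement says whom the study is about and is not an entry rule. Sampling prescribed users from a wider population would not contradict it. That is correct. The inconsistency rests on Table 1 and the explanations of its criteria.

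Fourth, there are other protections: researchers trained in first aid, a defibrillator, an emergency room about 250 m away, an emergency action plan, foreseeable risks stated in the consent form, and a physician able to be on site within ten minutes on experimental days. These reduce the weight of the point. The physician cover is worded for experimental days, whereas Procedures calls day one a screening day, so it is not clear that it extends to the first dose.

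**Conclusion.** The inconsistency holds. The risk section claims a safeguard that 0 of the 10 listed criteria impose, and the one criterion that mentions salbutamol meets only one of the two stated grounds. A person with diagnosed asthma and/or EIB, no salbutamol prescription and no known allergy to it can satisfy the whole list and be dosed from day one.

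The conclusion rests on reading Table 1 and its explanations as the complete eligibility list, as the text presents them, and on not assuming that a diagnosis implies a prescription, which the documents never say. The number of people affected is unknown.

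The consequence is limited. Known allergy is excluded and emergency provisions are described. Each participant is to take all four conditions, so the within-person comparison is not biased. The point should be corrected because it concerns a stated safety protection and the definition of the enrolled population.

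**What to change.** Reconcile Table 1 and its explanations with the salbutamol paragraph of Ethical Considerations so that both state the same rule on prior prescription, and make screening follow whichever rule is kept. Because salbutamol is first given on day one, any eligibility check that depends on this rule has to come before that dose. The documents do not show which version was intended, and the choice belongs to the investigators and the ethics board.

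The cost is about one line of text, in the eligibility list or in the risk section. If the prescription limit is kept, the recruitment pool may be smaller; the documents give no figure for how much.
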